Full Study Protocol and Statistical Plan

Study Title: A Clinical Risk Score for Early Management of TB in Uganda
(NIH/NIAID R21AI161301, PI: [name])

NCT Number: NCT05122624

Date of the document: August 03, 2021

1.SIGNIFICANCE

Tuberculosis (TB) remains the leading cause of mortality, causing over 1.4 million deaths in 2018.¹ A major contributor to TB mortality is underdiagnosis and undertreatment³— particularly in resource-limited primary health clinics. In these settings, up to 40% of patients diagnosed with TB are either lost to care before starting treatment or have treatment substantially delayed.³ Data from our study site in Kampala, Uganda, confirm this finding:¹³ 45% of patients who test positive for TB by Xpert MTB/RIF (“Xpert”, Cepheid, Inc., Sunnyvale, CA, USA) remain untreated one week later. Patients who are diagnosed with Xpert-positive TB and yet remain untreated are at great risk of both transmission and mortality.¹⁴ Many of these infections¹⁵ and deaths¹⁶ could be averted if TB treatment were initiated on the same day as initial presentation.

The most straightforward way to provide same-day TB treatment initiation is to offer same-day microbiological diagnosis, as recommended by the World Health Organization (WHO).¹⁷ Point-of-care Xpert testing shortens time to treatment^{18,19} and in rural Malawi,²⁰ reduced all-cause mortality among patients newly diagnosed with advanced HIV. Similarly, same-day testing and treatment initiation for HIV has been demonstrated to improve patient outcomes, both short-term (e.g., >25% increase in 3-month linkage-to-care)²¹ and longer-term (e.g., 18% increase in 12-month viral suppression)⁴, relative to testing with delayed treatment initiation. However, implementation of same-day Xpert testing is not feasible in many highly resource-limited settings, which often lack the necessary infrastructure and financial resources.^{14,22-24} In these settings, confirmatory TB testing may take days to weeks, and the risk of pre-treatment loss-to-follow-up is high.^{3,25} If global targets (e.g., 90% TB mortality reduction by 2035)²⁶ are to be met, there is therefore an urgent need to improve TB management in these most-resource-constrained clinics where same-day microbiological testing is infeasible.

When same-day diagnosis cannot be made, clinicians must balance the risks and benefits of same-day empiric treatment initiation. For many diseases – including gonorrhea²⁷, chlamydia²⁸, and urinary tract infections²⁹ – same-day empiric treatment (after an initial risk assessment) is commonly prescribed, as the harms of treatment delay outweigh the harms of overtreatment. Same-day empiric treatment for TB, however, is uncommon – as the duration of treatment is at least six months, and the perceived harms of overtreatment are high.⁶ As a result of these perceptions, one common practice is to prescribe broad-spectrum antibiotics while awaiting the results of sputum TB testing – a practice that lacks a strong evidence base.³⁰ An alternative approach would be to perform a rapid TB risk assessment and prescribe same-day empiric treatment for TB to those at high risk. The harm of a missed TB diagnosis has been estimated at more than 30 times that of a false-positive diagnosis.⁵ Thus, same-day empiric treatment of TB could provide clinical benefit by preventing progression of symptoms (and perhaps mortality) and epidemiological benefit by preventing transmission (as effective treatment rapidly renders most patients non-infectious^{31,32}). Despite its potential to greatly improve patient and population outcomes, same-day empiric treatment of TB in settings where same-day confirmatory diagnosis is unavailable would represent a major shift in the clinical management of TB – a shift that would require a large cluster-randomized trial for confirmation. Prior to conducting a major clinical trial, it is essential to test the hypothesis that same-day empiric treatment improves clinical outcomes for patients with TB in the most resource-constrained settings.

A necessary precondition to implementing same-day empiric treatment for TB is the availability of a risk assessment that is sufficiently easy-to-use that it could be implemented in peripheral clinics in high-TB-burden settings.^{15,33} Unfortunately, most existing models for predicting active TB require equipment or infrastructure (e.g., radiology³⁴, laboratory testing³⁴⁻³⁷, stadiometer measurements^{36,37}, and calculations requiring a computer or smartphone³⁸) that are generally unavailable in clinical settings that lack same-day microbiological testing for TB. Other prediction models incorporate data only available in specific contexts (for example, household contact investigations^{39,40} or HIV clinics^{34,38}) and thus cannot be applied more broadly. Our team recently developed and validated a clinical risk score for pulmonary TB that easily calculable using pen and paper, employing only data that would be readily accessible to mid-level clinicians after a brief patient interview. This risk score has sufficiently high accuracy to improve clinical decision-making (see Preliminary Data below) but has not yet been demonstrated to impact patient outcomes. The proposed study will generate these data, which are necessary before deciding whether to proceed with a larger cluster randomized clinical trial.

2.INNOVATION

This proposed study is innovative in terms of its intervention, setting, design, and clinical relevance:

- **Innovative tool:** We propose to evaluate a clinical risk score for pulmonary TB that was developed in rural South Africa and subsequently validated, in terms of accuracy and potential clinical utility, in urban

Uganda. This score has not yet been assessed in terms of implementation or effectiveness. This study will therefore be one of the first assessments of the clinical and epidemiological impact of a simple prediction rule designed to improve patient-important outcomes for TB in high-burden settings.

- **Innovative setting:** This clinical risk score has been explicitly designed for implementation in peripheral health clinics with minimal infrastructure. Very few clinical innovations have been created with the most-resource-constrained settings in mind.
- **Innovative study design:** We propose a highly pragmatic, hybrid implementation-effectiveness evaluation that will both provide an evidence-based justification for, and inform the implementation of, a subsequent cluster randomized trial of the impact of a clinical risk score on patient-important outcomes.
- **Potential to change clinical management:** This study is supported by the Ugandan National TB and Leprosy Program (see Letter of Support) and if successful (and confirmed in a subsequent trial) could effect a major change in the clinical management of pulmonary TB among the patients at greatest risk for catastrophic consequences, including long-term sequelae, mortality, and community transmission.

3.APPROACH

3.2. Preliminary Studies and Experience

3.2.1. The PredicTB Risk Score

Our team has developed a simple clinical risk score (“PredicTB”) for predicting active pulmonary TB in settings where same-day microbiological testing is not available (Figure 1). This score was developed using data from 1,387 adult patients who presented with classical TB symptoms (cough, fever, weight loss, night sweats) at 28 primary health clinics in rural Limpopo district, South Africa, and for whom a sputum Xpert test for TB was ordered.¹² We then externally validated this score using data from 387 patients who presented with TB symptoms and were

[figure not shown]

Figure 1. A simple clinical risk score (PredicTB) for initiation of empiric TB treatment when same-day testing is not available

tested using Xpert in four primary health clinics in Kampala, Uganda. This clinical risk score is designed for ease of use, being scored on a scale from 1-10 and using only readily accessible demographic and clinical data (sex, age, self-reported HIV status, self-reported diabetes status, number of symptoms, and duration of symptoms >14 vs ≤14 days; see Figure 1). The c-statistic for this easy-to-use risk score in the validation population was 0.75, consistent with other scores using more detailed clinical data,^{34–38} and decision curve analysis indicated that the net utility of using this score (at a cutoff of ≥5/10) would be significantly higher than no empiric treatment. As an example, a person with a PredicTB score of 7/10 in a population where 10% of all diagnostic Xpert tests are positive (i.e., pre-test probability of 0.1) would have a calculated 43% chance of having TB – a post-test probability that likely is sufficiently high to merit same-day empiric treatment. *De novo* development of a corresponding score in the Ugandan population resulted in very similar attributes being selected (diabetes was dropped and antiretroviral status plus observed cough were added), and very similar performance (validation c-statistic of 0.78).¹² This easy-to-use risk score is therefore sufficiently accurate to improve clinical decision-making in the most-resource-constrained settings; the proposed study will evaluate whether real-world implementation of this score can improve patient outcomes as well.

3.2.2. Impact of same-day diagnostic testing for pulmonary TB on patient outcomes in Uganda

Our team performed a comparison of patient outcomes comparing eight clinics with available Xpert testing on-site against 10 clinics using Xpert as an offsite referral test⁵⁴ (R21AI106031, PI: [name]). We found that the proportion of patients starting TB treatment was not significantly higher in clinics with on-site Xpert testing (11% vs 9%), and that a positive Xpert test changed management in fewer than 1% of all patients tested. We subsequently collaborated as part of a clinical trial (XPEL-TB, R01HL130192, PI: [name]) in which peripheral health centers were randomized to on-site Xpert testing versus off-site referral testing⁴⁴ for a period of 18 months. The design of this trial was highly pragmatic,⁵⁸ with minimal involvement of study staff in routine clinic activities, and the primary outcome assessed by way of ongoing record review (as also proposed for the present study). Preliminary results from this trial indicate that the number of individuals diagnosed and treated for microbiologically confirmed pulmonary TB within 14 days was 14.0 per clinic in the offsite testing arm versus 27.7 per clinic in the on-site testing arm (relative risk 2.0, 95% confidence interval 1.5-2.7) – a doubling of TB diagnoses made. Thus, in the off-site testing arm, more than half of all individuals with microbiologically confirmable TB were either never diagnosed or started on treatment with a delay of >14 days. Unfortunately, despite being a leader in Xpert procurement – with an estimated 526 Xpert modules procured by the end of 2016⁴⁶ – Uganda does not have capacity to offer on-site testing to the vast majority of its >3,000 peripheral level clinics.⁵⁹ These results indicate the urgent need for substantial improvement in TB management in the most-resource-constrained peripheral health clinics of Uganda and other high-TB-burden countries. They also demonstrate our team's ability to effectively measure patient-important TB outcomes using highly pragmatic study designs in this context.

3.2.3. Population-level impact of same-day TB treatment in Africa

In addition to the conduct of pragmatic clinical studies, our team also has expertise in modeling of long-term clinical and epidemiological impact of same-day TB treatment. For example, we used a compartmental mathematical model to estimate the impact of rapid TB treatment initiation in the WHO African Region. We projected that same-day treatment initiation could reduce annual TB mortality in sub-Saharan Africa by 44% within ten years.¹⁵ These projections highlight the substantial epidemiological gains that could be achieved by effective implementation of same-day TB treatment initiation in Uganda and other high-burden settings.

3.3 Research Design and Methods

3.3.1. Study setting and design

We will conduct this study in four primary health clinics in peri-urban Uganda (with four additional clinics serving as a comparison). Uganda is one of 30 high TB burden countries recognized by World Health Organization (WHO), with an estimated 2018 TB incidence of 200 per 100,000; 41% of those cases were co-infected with HIV.¹ Like many countries in East Africa, Uganda is among the world's poorest countries with an estimated per-capita gross domestic product (GDP) of \$777 2019;⁶⁰ the drivers of its TB epidemic are multifaceted,⁶¹ and there is relatively little drug resistance. Most TB in Uganda is diagnosed in public sector health facilities, and despite national guidelines promoting the use of Xpert, sputum smear microscopy remains the primary diagnostic assay used.⁵⁴ Diagnostic and treatment delays are common,⁶² resulting in a large number of untreated prevalent cases; the 2014-15 Ugandan National TB Prevalence Survey⁶³ estimated the prevalence of bacteriologically confirmed TB at 401 per 100,000 adults. These conditions are typical of sub-Saharan Africa (outside of South Africa); thus, findings from our study are likely to be broadly relevant.

We have selected four study clinics based on the following criteria: (a) within 150km of the capital city, Kampala; (b) no access to same-day Xpert testing (a criterion that effectively excludes clinics in Kampala proper); (c) high-quality TB record-keeping; (d) at least 100 bacteriologically confirmed TB cases diagnosed in 2019 (which effectively excludes private-sector clinics); and (e) clinic in-charge willing to have clinic staff trained in use of the PredicTB tool. We have also selected four comparison clinics that are similar in location and patient population to the four primary study clinics, but for which the latter two criteria were relaxed.

3.3.2. Study overview

The overall goals of this proposal are to estimate the effectiveness of the PredicTB clinical risk score in improving clinical outcomes for patients with pulmonary TB and to generate pragmatic data regarding the implementation of this score in highly resource-constrained primary health clinics. If successful, this study will provide an evidence base to justify the design and conduct of a larger cluster-randomized trial. This study will be conducted as a type 2 hybrid effectiveness-implementation evaluation. Our primary effectiveness outcome will be the difference in the proportion of adults with bacteriologically confirmed pulmonary TB who initiate treatment within 7 days of submitting sputum for TB diagnosis, comparing the 12 months before implementing

the PredicTB score to the 12 months after implementation. Secondary analyses will assess for the potential that measured differences reflect improved general practice and/or secular trends. Our primary implementation outcome will be the proportion of patients in the study clinics in whom the PredicTB score is used as indicated. Our study will consist of four phases (Figure 2): pre-implementation, implementation, post-implementation, and end phase. We will adopt a highly pragmatic study design in which we minimize involvement of study staff in the clinics under evaluation, with the exception of the intervention itself.

3.3.3. Study procedures

[figure not shown]
In the pre-implementation phase

(month -6 to month 6), study and comparison clinics (selected as already having high-quality TB records) will continue to maintain standard TB registers. These registers include all individuals who have sputum sent for TB diagnosis with sputum smear and/or Xpert ("presumptive register") and all individuals who are started on TB treatment ("treatment register"). We will abstract key data from these registers, including age, sex, prior TB treatment, HIV status, diagnostic result, and treatment outcome. During month 1 of the study, we will initiate a retrospective abstraction of all registers from month -6. We will also begin prospective abstraction of registers by having routine clinic staff take photos of registers and securely transfer them to our study team, who will upload these into a REDCap database. Staff from the XPEL-TB trial⁴⁴ have experience in these procedures (including the development of a pre-existing database for this purpose), so we will be able to initiate this abstraction rapidly and seamlessly.

In the **implementation phase** (month 7), we will train clinic staff in all eight clinics (study clinics and comparison clinics) on the Ugandan standard of care for diagnosis and treatment of TB. In addition, in the four study clinics, we will provide training on the PredicTB score. This training will include the following elements: (a) background on the PredicTB score and its aim of informing empiric treatment decisions for adult pulmonary TB; (b) provision of materials (paper score sheets and laminated instruction sheets) to enable clinicians to use the PredicTB score; (c) reinforcement that all treatment decisions are ultimately at the discretion of the treating physician; (d) reinforcement that PredicTB is not meant to be a replacement for microbiological testing – that sputum should be sent for microbiological testing in all patients presenting with symptoms of TB, and that any patient with a positive microbiological test should be treated for TB. Prior to this training, we will speak with the head (in-charge) physician at each of the four study clinics to describe the PredicTB score and elicit the physician's recommendations as to the percentage of TB tests that are positive in the clinic (i.e., columns in Figure 1) and the score that should be encouraged as a threshold for same-day empiric treatment initiation. Importantly, this threshold may vary from one clinic to another; our analyses will not explicitly incorporate this threshold as a covariate, but we will explore clinic-by-clinic variation by way of informing any future clinical trial. Furthermore, we will seek the in-charge physician's advice regarding an alternative approach in which patients with high (e.g., >40%) risk could be scheduled for a full treatment course, whereas those with intermediate (e.g., 10-40%) risk could be prescribed a provisional (e.g., 14-day) course, which could be discontinued if microbiological testing for TB was negative and the clinical course [e.g., full resolution in 1-2 days or continued worsening of symptoms despite TB therapy] were inconsistent with a diagnosis of TB. Training in the use of the PredicTB risk score in each clinic will therefore follow the recommendations of each clinic's in-charge physician and will only augment (not supplant) the Ugandan standard of care for TB management. We will re-evaluate these recommendations every three months during site visits (see below) and update training as needed.

In the **post-implementation phase** (months 7-18), we will encourage all eight clinics (study and comparison clinics) to continue high-quality record-keeping as during the pre-implementation phase. The four study clinics

Figure 2. Study Overview

will be asked to maintain records of the PredicTB score sheets for all patients on whom the score was calculated. We will also perform quarterly site visits that will include the following components:

- Review of the quality of record-keeping and transmittal of records to study staff [all clinics];
- Collection of cost data, including budgetary review and time-and-motion studies [study clinics];
- Assessment of PredicTB reach (proportion of patients receiving same-day empiric treatment initiation), adoption (proportion of clinicians adopting PredicTB), and implementation (proportion of patients in whom PredicTB was used as indicated) [study clinics]; and
- Performance feedback to clinic staff regarding TB diagnosis and treatment outcomes [all clinics].

During this phase, we will also perform mycobacterial culture (using both solid [Lowenstein-Jensen] and liquid [Mycobacteria Growth Indicator Tube, MGIT; BD Diagnostics, Sparks, MD, USA] media) on all sputum specimens from all eight clinics that are Xpert-negative but correspond to adult patients who were empirically initiated for TB. *These culture results will not be used for any of our primary effectiveness analyses* but instead will be used to estimate the sensitivity and specificity of empiric treatment decisions, both with and without the PredicTB score. Specimens will be sent from the central laboratories in which Xpert is performed, rather than from study clinics themselves, so as to minimize interference with study clinic procedures. Nevertheless, culture results will be transmitted back to clinicians to assist with management.

In the **end phase** (months 19-24), we will complete the statistical analysis of effectiveness (Aim 1) and implementation (Aim 2). We will also perform cost-effectiveness and impact analyses for Aim 3. In addition, in the four study clinics, we will conduct a series of 100 patient surveys (25 per clinic) in which we recruit, consent, and enroll consecutive patients in each clinic who submit sputum for TB testing. For these patients, study staff will independently administer the PredicTB score and will also assess the following: (a) treatment decisions and patient motivation to complete treatment; (b) additional TB risk factors (e.g., smoking status, observed cough, antiretroviral therapy, symptom duration/severity, body mass index); (c) patient socioeconomic status, transit time to clinic, and cost of attending clinic; and (d) patient opinions regarding the value of same-day empiric TB treatment. These additional data will enable us to consider refinements to the PredicTB model (both content and implementation) in preparation for a potential future large-scale trial.

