This analysis is subject to bias resulting from both secular trends and non-intervention-related effects. We will therefore also perform a difference-in-differences analysis, comparing pre-post effects in the study clinics to those observed in the comparison (non-PredicTB) clinics (Aim 1c). We have not made this our primary analysis because the comparison clinics are smaller (thereby reducing power) and not randomly allocated – for example, staff in these clinics may be less motivated to change behavior. We will also perform a parametric regression discontinuity analysis to estimate the causal effect of implementing the PredicTB risk score (with the discontinuity occurring at the time of implementation). This analysis, however, has less statistical power, and the shape of the effectiveness curve over time in the post-implementation period may reflect important effects (i.e., we are interested not only in the immediate effect of the intervention but also its maintenance over time).

Sample size considerations. Based on patient volumes in 2019, we anticipate a sample size of 1100 patients with confirmed TB: 550 pre-intervention and 550 post-intervention. Using data from our STOMP-TB study,¹³ we expect that 55% of patients will initiate treatment within 7 days in the pre-intervention period. Assuming a design effect of 1.67 due to clustering by clinic, we will have 80% power to detect a difference if treatment initiation increases to 66% in the post-intervention phase and 97% power if treatment initiation increases to 70% (Figure 3).

[figure not shown]

Figure 3. Study power

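### Month 7 is both the training month and the first post-implementation month, with no transition rule, so untrained time can be counted as exposed

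*Combined protocol and SAP*

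**What the plan says.** Section 3.3.3 assigns month 7 twice. The implementation phase is that month: "month 7), we will train clinic staff in all eight clinics". The four study clinics also receive their PredicTB training and score sheets then. The next phase, post-implementation, is given as "months 7-18), we will encourage all eight clinics (study and comparison clinics) to continue high-quality record-keeping".

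Section 3.3.2 sets the primary effectiveness contrast as the 12 months before "the PredicTB score to the 12 months after implementation". Section 3.3.4 (Aim 1) identifies the two periods by the shading in Figure 2, which is not available to us. Section 3.3.4 also plans a difference-in-differences analysis, a parametric regression discontinuity analysis with its break at the time of implementation, and (Aim 2) a maintenance measure running from month 7 to month 18. The end phase in Section 3.3.3 begins in month 19.

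The sample size paragraph in Section 3.3.4 assumes "550 pre-intervention and 550 post-intervention" patients with confirmed TB. It adds that "we expect that 55% of patients will initiate treatment within 7 days in the pre-intervention period". Clustering is allowed for with a design effect of 1.67. Power is put at 80% for the first of two scenarios, and both are worded as follows: "treatment initiation increases to 66% in the post-intervention phase and 97% power if treatment initiation increases to 70" (per cent).

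**The concern.** Months 7 to 18 make 12 months only if the training month counts as after implementation. Clinicians cannot use the score before they have been trained and given the sheets, so any study-clinic patient seen earlier in month 7 is unexposed. Nothing in the visible text keeps such patients out of the post period.

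If PredicTB works, this pulls the primary difference towards zero. It matters more where month 7 carries extra weight: in the discontinuity analysis it lies at the break, and in the maintenance measure it is the baseline. If the boundary is not fixed beforehand, it would also have to be chosen once data are in hand.

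**Working it through.** **Inputs.** From the sample size paragraph in Section 3.3.4: 550 patients per period, 55% before, 66% or 70% after, design effect 1.67. Assumed here, because the plan does not state them: two-sided alpha 0.05 and even monthly flow (550/12, about 46 confirmed patients a month).

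**1. The plan's own power.** Effective n per period = 550/1.67 = 329.3. With d the difference, SE0 the pooled standard error under the null and SE1 the unpooled one, power = Φ[(d − c − 1.96·SE0)/SE1], where c = 1/n with continuity correction and 0 without.

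For 55% vs 66%: SE0 = √(2 × 0.605 × 0.395/329.3) = 0.0381 and SE1 = √((0.2475 + 0.2244)/329.3) = 0.0379. Power is 80.3% with correction and 82.5% without. For 55% vs 70% it is 97.5% and 97.9%. The stated 80% and 97% reproduce with the correction.

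**2. Dilution of the primary difference.** If a fraction f of month 7 is unexposed, the expected difference is 11 × (1 − f/12) points.
- f = 1: 11 × 11/12 = 10.1 points
- f = 0.5: 11 × 11.5/12 = 10.5 points

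**3. Power under two meanings of 66%.** If 66% is the whole-period average, untrained time is already inside it and step 1 stands unchanged. If 66% is the rate once training is complete:

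| Handling of month 7 | Post-period rate | Power, corrected | Power, uncorrected |
|---|---|---|---|
| Kept, wholly unexposed | 65.1% | 72.8% | 75.3% |
| Kept, half unexposed | 65.5% | 76.7% | 79.1% |
| Kept, a quarter unexposed | 65.8% | 78.6% | 80.8% |
| Dropped, 550 vs about 504 (550 × 11/12) | 66% | 78.4% | 80.7% |
| Replaced by a 12th full month | 66% | 80.3% | 82.5% |

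In the 70% scenario with month 7 wholly unexposed, power is 94.6% (corrected) or 95.4% (uncorrected).

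**4. Regression discontinuity.** Assume 12 equally weighted months per side, a separate straight line on each side and a constant 11-point step. Number the post months 1 to 12: mean 6.5, sum of squares 143. The weight of the first month in the fitted value at position x is 1/12 + (x − 6.5)(1 − 6.5)/143.
- Break at the start of month 7 (x = 0.5): weight 0.083 + 0.231 = 0.314. An unexposed month 7 removes 11 × 0.314 = 3.5 points, leaving about 7.5.
- Break at the month-7 point (x = 1): weight 0.083 + 0.212 = 0.295. The loss is 3.2 points, leaving about 7.8.
- Half exposed: the loss halves, leaving about 9.3 with the break at the start of month 7.

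**5. Maintenance.** On the same straight-line basis, an unexposed first month adds a slope of 11 × 5.5/143 = 0.423 points a month. Over the 11 intervals from month 7 to month 18 that is a false rise of about 4.7 points, or 2.3 if month 7 is half exposed. The plan does not say how this change is to be estimated, so the straight line is an assumption.

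**The case against.** Several points on the other side stand. Dilution is possible, not certain: the day of training is not given, Figure 2 may mark the boundary, and 12 months after implementation, read literally, excludes pre-training days. The figures for a wholly unexposed month 7 are worst cases, and the primary bias is at most 0.9 of 11 points, towards no difference. In the plan's 70% scenario power stays near 95% throughout.

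A reader might infer that the study misses its stated 80% power. The documents do not support that. The calculation reproduces, and 66% is stated for the post-intervention phase, not for time after training is complete. The shortfall in step 3 needs a meaning of 66% that the plan does not give.

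It can also be said that a pragmatic study may properly include early roll-out. That is a defensible target, but the plan does not state it. It would not suit the discontinuity analysis, which is meant to isolate the effect of implementation.

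Finally, dropping month 7 gains little power: 78.4% against 76.7% with half exposure kept (corrected). That is true, but the case for dropping it is bias, not power. Extending to month 19 has a real cost. Month 19 opens the end phase, in which study staff administer the score themselves to surveyed patients in the study clinics.

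**Conclusion.** The overlap is in the plan's text and should be resolved. Its effect on the primary difference is small: at most 1/12 of the effect, or 11 points down to 10.1, under even monthly flow. The difference-in-differences estimate has the same overlap. The consequence is larger for the discontinuity analysis, where 11 points can be estimated as about 7.5 (9.3 with half exposure), and for maintenance, where a false rise of up to about 4.7 points could mask real waning. These last two figures rest on equal monthly weights, straight-line fits and a constant effect.

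The stated 80% power stands as worded. Only if 66% was meant as the post-training rate does it fall, to about 73-75% with month 7 wholly unexposed or 77-79% with half exposure, assuming two-sided alpha 0.05.

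**What to change.** Define month 7 as a transition month. Exclude it from the primary pre-post, difference-in-differences and discontinuity analyses, and start the maintenance measure at month 8. Report the analysis including month 7 as a sensitivity analysis. State whether 66% is a period average or a post-training rate.

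Two post periods are workable:
- **Months 8-18.** No new data collection. Power for 55% vs 66% is about 78-81%, the post period is one month shorter and the exact 12-month match is lost.
- **Months 8-19.** This keeps 12 months and power of 80-82%, but only if the end-phase patient surveys in the study clinics start after month 19. It costs one more month of register abstraction and a later survey start.

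Either choice is a wording change to Sections 3.3.3 and 3.3.4, best made before outcome data are examined.
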